#### 8.8 Visit 6 End-of-Treatment (EOT) or Early Withdrawal (Week 16 $\pm 7$ days) Visit

For participants who have completed the maintenance phase or who have withdrawn early from the study, the following procedures will be performed in the clinic:

- Conduct vitals (blood pressure, heart rate, respiratory rate, temperature), height, and weight
- Physical exam
- Administer patient- and parent-reported outcome questionnaires
- Clinical laboratory samples, including CBC with differential, chemistry, and IgE
- Research laboratory samples

- Urine pregnancy test in females of childbearing potential
- Assess AEs
- Assess changes to concomitant medication/therapies
- Obtain esophageal biopsies including biopsies taken for clinical purposes and up to 4 biopsies from the distal esophagus for research purposes obtained from standard of care (SOC) endoscopy
- Assess participant compliance with diet
- Collect diet and medication log
- Collect study agent bottle and unused study agent
- Determine participant's compliance with the study agent

The EOT visit may be divided into two appointments, if necessary, in order to allow for all necessary procedures to be performed. Participants who have completed the maintenance phase should be instructed not to take the study agent on the day of this visit; the last dose of study agent should be taken the day prior to the EOT visit. If a participant withdraws from the study before completing the maintenance phase, the EOT/early withdrawal visit, including EGD and biopsy, should be conducted within one week of the participant's last dose of the study agent.

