#### 8.9 Visit 7 Follow-Up Call/Visit (Week 20 ± 7 days)

The research personnel will conduct a follow-up safety telephone call to the participant 30 ± 7 days after the last dose of the study agent. Females of childbearing potential will have their urine pregnancy test conducted in the clinic. The call/visit will consist of the following procedures:

- Administer patient- and parent-reported outcome questionnaires
- Assess AEs
- Assess concomitant medications
- Assess diet and concomitant medication
- Urine pregnancy test in females of childbearing potential

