g EndoFLIP is a SOCEvaluation for esophageal dysmotility, done at the same time as their endoscopy.

h The data gathered from these questionnaires will be correlated with several biomarkers of interest that have been associated with EoE. Each visit window (for visits 1-7) is  $\pm 7$  days.

i Urine pregnancy tests will be performed in females of childbearing potential on a monthly basis at each visit (except phone calls) and will be performed in the clinic.

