#### 2. Secondary Outcomes

- Change from baseline in the blood (serum) and esophageal TGF- $\beta$  levels in participants receiving losartan at the EOT visit (or at early withdrawal) as determined by research blood samples and EGD with biopsy, respectively.
- Normalization of the EoE transcriptome in participants receiving losartan at the EOT visit (or at early withdrawal) as determined by EGD with biopsy.
- Change from baseline in histopathology in participants receiving losartan at the EOT visit (or at early withdrawal) as determined by EGD with biopsy.
- Change from baseline esophageal compliance in participants receiving losartan at the EOT visit (or at early withdrawal) as determined by EndoFLIP.
- Change from baseline PROS (Pediatric Eosinophilic Esophagitis Symptom Severity [PEESS], PedsQL Eosinophilic Esophagitis Module [PedsQL™ EoE], EoE Quality of Life Questionnaire, and EEsAI) in participants receiving losartan at the EOT visit (or at early withdrawal).

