Additionally, to evaluate the effect of losartan on the reduction of esophageal eosinophils in participants with EoE (with or without a CTD), we will use paired non-parametric Wilcoxon Rank sum test. The Wilcoxon rank sum paired test will be used given the small sample size and the broad range of eosinophils which could be present in our participants. Analyses will be performed using the whole cohort and stratified by CTD. Statistical significance will be set at $\alpha = 0.05$. This corresponds to testing the following hypothesis:

H0: baseline and study completion are equal vs. H1: baseline and study completion are not equal.

Analyses of Secondary Endpoint(s)/Outcome(s)

To assess changes over time for continuous secondary and safety outcomes, a mixed effects model for repeated measures analysis will be used. The dependent variable will be the change from baseline. The “participant nested within group” term will be considered a random effect. Time (i.e. measurement time) will be included as a continuous effect. Terms in the model will be time, group (i.e., EoE and EoE-CTD), and time-by-group interaction. The baseline value will be used as a covariate in the model. If necessary, to meet the assumptions of the analysis, an appropriate transformation will be used (e.g., square root, log, rank). The hypotheses that will be tested are whether there is a significant trend over time and whether this trend is consistent between the CTD and non-CTD groups (i.e. testing the interaction term). If the trend is not consistent between groups based on the statistical test at $\alpha=0.10$, we will estimate the trend within each of the two groups by including terms in the statistical model that estimates the trend within each group and the hypothesis to be tested within each group is whether this trend is significantly different than zero. We will systematically assess the residuals to determine whether a linear or quadratic model best fits the data. In statistical terms, the hypotheses are provided below.

For testing consistency of the time trend (β) between the CTD and non-CTD group, the hypotheses are:

H0: $\beta_{\text{EoE-CTD}} = \beta_{\text{EoE (non-CTD)}}$ vs. H1: $\beta_{\text{EoE-CTD}} \neq \beta_{\text{EoE (non-CTD)}}$.

For testing linear trend combining across groups (if there is consistency of the time trend):

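### The SAP sets no last visit for the questionnaire trend model, so off-drug Week 20 scores can enter and cancel, shrink or reverse the on-drug slope

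*SAP*

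**What the plan says.** **Schedule.** Table 4 of the protocol marks all four questionnaires (PEESS, PedsQL EoE, EEsAI and the adult EoE quality-of-life instrument) at Weeks 0, 4, 8, 12, 16 and 20. Section 8.8 says that for completers "the last dose of study agent should be taken the day prior to the EOT visit". Section 8.9 places the follow-up contact "30 ± 7 days after the last dose of the study agent" and lists among its procedures "Administer patient- and parent-reported outcome questionnaires". Of the five post-baseline questionnaire times, four are on drug and one is off drug.

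**Endpoint.** Protocol 12.2.2 defines the questionnaire outcome as change from baseline "in participants receiving losartan at the EOT visit (or at early withdrawal"). Week 20 is not part of it. The SAP's own list of secondary outcomes gives the questionnaires no time point.

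**Model.** The SAP (Analyses of Secondary Endpoint(s)/Outcome(s)), with the same text in Protocol 12.4, specifies a mixed model: "The dependent variable will be the change from baseline", with baseline as a covariate, and "Time (i.e. measurement time) will be included as a continuous effect". It then states: "The hypotheses that will be tested are whether there is a significant trend over time", together with a test of whether the trend agrees between the two groups. Residuals are to guide a choice between a linear and a quadratic form. No visit is named as the last to enter, and no term separates on-drug from off-drug assessments.

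**The concern.** The endpoint asks what happened to symptoms by the end of treatment. A slope over every scheduled post-baseline visit asks something else, because its last point is measured about a month after the drug stops. If symptoms improve on losartan and return afterwards, which would itself suggest a drug effect, the Week 20 score pulls the linear slope toward zero or past it.

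Among the efficacy secondary outcomes, only the questionnaires have more than one post-baseline time, so for efficacy this slope is in effect the questionnaire analysis. The SAP also intends the slope's confidence interval to inform later studies. A slope that mixes on-drug and off-drug data would be carried into their design.

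**Working it through.** The documents give no slope, SD or power for the questionnaires, so there is no stated figure to reproduce.

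**Inputs from the documents:** post-baseline times 4, 8, 12, 16 and 20 weeks (Table 4); last dose the day before the Week 16 visit (8.8); 15 participants (Protocol 12.5); two-sided alpha 0.05.

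**Assumptions:** the response is scaled so that improvement is negative and the Week 16 value is -1; complete data; the same shape in both groups. The shape of the response and the share kept at Week 20 are varied.

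**Formula.** With balanced data, the time slope of a random-intercept model equals the least-squares slope, Σ(t − t̄)y / Σ(t − t̄)².

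*Weeks 4–16:* t̄ = 10, deviations -6, -2, 2, 6, sum of squares 80. For a linear gain (-0.25, -0.5, -0.75, -1) the numerator is 1.5 + 1 − 1.5 − 6 = -5, so the slope is -5/80 = -0.0625 per week.

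*Weeks 4–20:* t̄ = 12, deviations -8, -4, 0, 4, 8, sum of squares 160. For the same gain the numerator is 2 + 2 + 0 − 4 + 8·y₂₀ = 8·y₂₀, so the slope is 0.05·y₂₀, where y₂₀ is the Week 20 value.

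| Shape on drug | Kept at Week 20 | Slope, Weeks 4–16 | Slope, Weeks 4–20 |
|---|---|---|---|
| Linear to Week 16 | all | -0.0625 | -0.050 |
| Linear to Week 16 | half | -0.0625 | -0.025 |
| Linear to Week 16 | none | -0.0625 | 0 |
| Half at Week 4, full from Week 8 | half | -0.0375 | 0 |
| Half at Week 4, full from Week 8 | none | -0.0375 | +0.025 |
| Full from Week 4 | all | 0 | 0 |
| Full from Week 4 | none | 0 | +0.050 |

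A positive slope means apparent worsening. If a baseline row of zero were also entered, the linear gain with full loss would give -5/280 = -0.018 instead of 0.

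**Illustrative power for the linear shape.** With residual SD 1 and a Week 16 response of 1 SD, the slope's standard error is 1/√(15·80) = 0.0289 on Weeks 4–16 and 1/√(15·160) = 0.0204 on Weeks 4–20. Slope over standard error is 2.17 on drug. With Week 20 added it is 2.45, 1.22 or 0 for all, half or none kept. Simulation (20,000 runs) gives these rejection rates:

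| Week 16 response (residual SDs) | Slope, Weeks 4–16 | Slope, Weeks 4–20: all / half / none kept | Quadratic term, Weeks 4–20: half / none kept |
|---|---|---|---|
| 0.5 | 18% | 23% / 9% / 4% | 12% / 24% |
| 1.0 | 56% | 67% / 21% / 3.5% | 32% / 71% |
| 1.5 | 89% | 95% / 39% / 2% | 62% / 96% |

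For a response complete by Week 4 and wholly lost by Week 20, at 1 SD, the linear test on Weeks 4–20 rejects in 64% of runs, essentially all in the direction of worsening.

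**The case against.** **Pooling is not stated.** A reader might infer that the SAP expressly analyses Week 20 as treatment data. It does not. The endpoint is tied to EOT, Table 4 puts Week 20 in a follow-up phase and labels it a safety call, and the SAP describes a 16-week trial. Leaving Week 20 out is a reasonable reading. This stands as a limit on the point. Still, a repeated-measures model in measurement time, with no cut-off, most plainly takes every scheduled post-baseline score. Where the authors wanted one visit they named it, as for the proportion below 15 eosinophils/HPF at Week 16. The SAP's analysis population restricts participants, not visits.

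**The quadratic step may catch a rise and fall.** For a linear gain of 1 SD that is fully lost, the quadratic term is significant in 71% of runs and a joint test of both terms in 59%, against 56% for the on-drug slope. So the low linear-only figures do not describe the whole planned procedure. But the SAP gives no criterion for choosing the quadratic form, detection falls to 32% when half the benefit is kept, and curvature does not estimate the on-drug change at EOT.

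**The result depends on shape.** A reader might also infer that any response that fades is tested as no trend. An exactly zero slope needs particular shapes; others give a reduced or reversed slope. Nor does Week 20 have uniquely high leverage: on Weeks 4–20 it ties with Week 4, at 1/5 + 64/160 = 0.6 each.

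**Scope is narrow.** The trial is a descriptive pilot whose size was not set by power. Table 4 schedules no biopsies, laboratory tests (other than a urine pregnancy test) or vital signs at Week 20. This is correct and limits the reach of the point, not its validity for the questionnaires.

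**Conclusion.** The point holds in a limited form. The plan leaves open whether off-drug Week 20 questionnaires enter the trend model, and its literal wording lets them in, against an endpoint defined at EOT. If they enter, the linear slope is distorted by an amount and in a direction that depend on the time course. For a linear gain, 80%, 40% or 0% of the on-drug slope remains (0.050, 0.025 or 0 over 0.0625) when all, half or none of the benefit is kept; for earlier responses the sign can reverse. The documents do not support saying that pooling is specified, or that a fading response is always tested as no trend.

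The slopes are exact for the assumed shapes. The power figures are illustrative only, because the documents give no questionnaire SD, effect size or time course after the drug stops. The primary eosinophil endpoint and the other secondary efficacy outcomes are untouched. The SAP should be changed, because the choice affects the result and costs almost nothing to settle in advance.

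**What to change.** Add to the SAP that the questionnaire model uses on-treatment assessments only: Weeks 4, 8, 12 and 16/EOT. For an early withdrawal, the early-withdrawal visit serves as EOT, as the endpoint provides, and the later follow-up contact counts as off treatment.

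Preferably, make the Week 16/EOT change from baseline with its 95% CI the reported estimate, for example by treating visit as a category. Restricting visits alone does not help a response that is complete by Week 4 and then held: its on-drug slope is zero, and the linear test rejects at about the 5% level. Report Week 20 minus EOT separately, with a 95% CI, as a description of what happens off drug.

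The cost is a short SAP addition and no new data. The trend loses one visit per participant. If the benefit were in fact fully kept at Week 20, power for the slope would be about 56% instead of 67% under the assumed linear gain of 1 SD.

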### 3.5 Exploratory Endpoint(s)/Outcome(s)

Serum and esophageal tissue will be collected from all participants at screening and at the EOT visit (or at early withdrawal) for the determination of TGF- $\beta$  levels and eosinophils. Exploratory laboratory tests will be analyzed by the research personnel in the [REDACTED].

Participants are not required to fast prior to the blood draw.

The total volume of blood collected for exploratory laboratory tests will be approximately 17.5 mL per visit (screening and EOT/early withdrawal). At any time during the study, the amount of blood collected from the participants will not exceed 5% of the estimated total blood volume over a 24-hour period per institutional policies. All blood and specimen collection and handling will be done in accordance with the institution's laboratory and infection control policies.

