### 4. Analysis Plan

Change from baseline for eosinophil counts will be calculated for each participant. The average change from baseline within each group and combining both groups (i.e. EoE and EoE-CTD) will be calculated along with the corresponding two-sided, 95% confidence intervals. If the assumption of normality is not viable for the change from baseline score, we will use a square root transformation on the eosinophil counts prior to calculating the change from baseline and determine if the "change score" attains normality. If this transformation is not successful, the median of the change will be calculated along with the 95% confidence interval for the median using Hodges-Lehmann estimators. Each confidence interval will be visually inspected to determine if zero is a possible value for the true change from baseline ( $\mu$ ). This corresponds to testing the following hypothesis:

$H_0: \mu=0$  vs.  $H_1: \mu \neq 0$ .

The last observation carried forward (LOCF) method will be used for participants who end the trial early.

To assess changes over time for continuous secondary and safety outcomes, a mixed effects model for repeated measures analysis will be used. The dependent variable will be the change from baseline. The "participant nested within group" term will be considered a random effect. Time (i.e. measurement time) will be included as a continuous effect. Terms in the model will be time, group (i.e., EoE and EoE-CTD), and time-by-group interaction. The baseline value will be used as a covariate in the model. If necessary to meet the assumptions of the analysis, an appropriate transformation will be used (e.g., square root, log, rank). The hypotheses that will be tested are whether there is a significant trend over time and whether this trend is consistent between the CTD and non-CTD groups (i.e. testing the interaction term). If the trend is not consistent between groups based on the statistical test at  $\alpha=0.10$ , we will estimate the trend within each of the two groups by including terms in the statistical model that estimates the trend within each group and the hypothesis to be tested within each group is whether this trend is significantly different than zero. We will systematically assess the residuals to determine whether a linear or quadratic model best fits the data. In statistical terms, the hypotheses are provided below.

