H0: $\beta=0$ vs. H1: $\beta\neq 0$ where β is the slope of the line across groups. Similar hypotheses will be tested if analysis of the residuals indicates that higher order terms need to be included in the model (e.g. quadratic). If there is strong evidence that the time trend is not consistent between the two groups, we will test the above hypothesis within each of the two groups. In addition, the two-sided, 95% confidence interval for the slopes will be calculated to provide estimates of the slope for future studies.

The percentage of participants for whom peak eosinophil counts are < 15 eosinophil/HPF at Week 16 will be estimated within each CTD group along with a 95% confidence interval.

Safety endpoints that are categorical will be summarized within each group. Further, any SAEs or Grade 3 or above will be reported descriptively.

Software Used (with References) and Specialized Macros (with References)

SAS version 9.4, JMP 14.

This SAP has been reviewed and approved by:

Investigator

Date

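### The model for continuous secondary and safety outcomes tests only a time slope of change scores: not estimable for TGF-β, HSS and EndoFLIP, and not a test of change from baseline for PROs and safety measures

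*SAP*

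**What the plan says.** SAP, Analyses of Secondary Endpoint(s)/Outcome(s), and Protocol 12.4 give one mixed model for all continuous secondary and safety outcomes. On the response: "The dependent variable will be the change from baseline". On time: "Time (i.e. measurement time) will be included as a continuous effect". The other terms are group (EoE, EoE-CTD), time-by-group, the baseline value and a random participant effect.

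On inference: "The hypotheses that will be tested are whether there is a significant trend over time", and whether that trend is the same in both groups. The null hypothesis is β = 0 with β defined as a slope, and confidence intervals are promised for slopes only. There is a quadratic extension: "Similar hypotheses will be tested if analysis of the residuals indicates that higher order terms need to be included in the model".

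The endpoints are worded differently. Protocol 12.2.2 has, for example, "Change from baseline in histopathology in participants receiving losartan at the EOT visit (or at early withdrawal) as determined by EGD with biopsy". TGF-β, EndoFLIP and the PROs are likewise changes from baseline at EOT; only the transcriptome endpoint (normalization) is not.

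The sampling schedule matters here. Protocol 3.5: "Serum and esophageal tissue will be collected from all participants at screening and at the EOT visit (or at early withdrawal"). Protocol Table 4 marks EGD and EndoFLIP at screening and Visit 6 only, with the footnote "EndoFLIP is a SOCEvaluation for esophageal dysmotility, done at the same time as their endoscopy". PROs are collected at Weeks 0, 4, 8, 12, 16 and 20; labs and vitals after baseline at Weeks 4, 8, 12 and 16.

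**The concern.** A slope of change scores and a mean change from baseline are different quantities, and the plan tests only the first while defining its endpoints by the second.

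- **One post-baseline time (TGF-β, HSS, EndoFLIP; also the transcriptome if it is scored continuously, which is not stated).** Each participant contributes one change score, at Week 16. Time is then constant, so it duplicates the intercept, and time-by-group duplicates group. The participant variance cannot be separated from residual error.
- **Repeated outcomes (PROs, labs, vitals).** The slope can be estimated, but a change that appears early and holds has zero slope. The quadratic option adds curvature, and a held effect has none.
- **Visits entering the model.** These are not stated. Week 20 PROs are collected about 30 days after the last dose (Protocol 8.9). If they enter, loss of benefit after stopping treatment pulls the line towards worsening.

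At stake are at least three of the five secondary endpoints, which have no workable stated analysis, and PRO results that could be reported as no significant trend despite a real change.

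**Working it through.** **The plan's own figures.** The documents give no power or precision figure for this model. Protocol Table 7 gives mean-change CI half-widths for eosinophils, which reproduce as t(0.975, n−1) × SD/√n. With SD 5: n = 15, 2.145 × 5/√15 = 2.77; n = 10, 2.262 × 5/√10 = 3.58; n = 5, 2.776 × 5/√5 = 6.21. The table prints 2.8, 3.6 and 6.2.

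**Inputs from the documents.** 10 EoE and 5 EoE-CTD participants (Protocol 12.5); visit times from Table 4; windows of ±7 days (Protocol 8.11); two-sided α = 0.05.

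**1. Single-time endpoints, nominal time.** The columns are [1, time, group, time × group, baseline] with time = 16 throughout. Time = 16 × intercept and time × group = 16 × group, so the rank is 3 of 5. What remains is intercept, group and baseline, which is a baseline-adjusted mean-change model.

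**2. Single-time endpoints, actual dates.** Assume visit times uniform over ±1 week (variance 1/3) and a change-score SD of 1. After fitting intercept, group and baseline, 12 degrees of freedom remain, so the time sum of squares is about 12 × 1/3 = 4 and the slope SE about 1/√4 = 0.50 SD per week (simulated median also about 0.50). Over 16 weeks that is 8 SD, against an SE of 1/√15 = 0.26 SD for the mean change. With a uniform 1-SD change (4,000 runs), the slope test rejects 5.1% and the adjusted mean-change test 94.1%.

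**3. Early leavers.** Protocol 8.8 says that for them "the EOT/early withdrawal visit, including EGD and biopsy, should be conducted within one week" of the last dose. With one leaver at Week 8 and no jitter, the slope is that person against everyone else (SE 0.14 SD per week) and the interaction is never estimable. With two leavers the SE is 0.10, and the matrix has full rank only when the two fall in different groups: 10 × 5/105, or about 48% (47% in simulation).

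**4. Repeated outcomes, Weeks 4 to 16.** Assumptions, not from the documents: n = 15, between-participant SD 1.0, residual SD 0.7, Week-16 effect equal to 1 SD of the change score, √(1.0² + 0.7²) = 1.22. Mean time is 10 and Σ(t − 10)² = 80, so the slope SE is 0.7/√(15 × 80) = 0.0202 per week. Rejection rates are from 20,000 simulated trials.

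| Fraction of effect at Weeks 4, 8, 12, 16 | Expected slope/week | Slope ÷ SE | Slope test | Joint linear + quadratic | Week-16 mean change |
|---|---|---|---|---|---|
| 1, 1, 1, 1 (held) | 0 | 0 | 5% | 5% | 95% |
| ½, 1, 1, 1 | 0.0458 | 2.27 | 57% | 68% | 95% |
| ½ rising linearly to 1 | 0.0509 | 2.52 | 70% | 57% | 95% |
| ¼, ½, ¾, 1 (linear from baseline) | 0.0763 | 3.78 | 96% | 92% | 95% |

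With between/residual SDs of 0.7/0.7, 0.7/1.0 and 1.0/0.5, the held effect stays at 5% (its slope is zero whatever the SDs), the second pattern ranges over 33–78% and the last over 74–99.8%.

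**5. If Week 20 is included.** Mean time is 12 and Σ(t − 12)² = 160. A held effect of 1.22 that is half lost (0.61) at Week 20 gives a slope of 8 × 0.61/160 = 0.030 per week towards worsening. It is significant in 52% of runs, and the quadratic term in 42%.

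**The case against.** - **Paired tests.** The SAP overview mentions paired tests of baseline against completion without naming an outcome, so secondary endpoints might be covered. But the sentence sits within the eosinophil text, the next assignment of secondary outcomes is to the mixed model, and the only detailed specification is for eosinophils. If wider use was meant, the SAP has to say so.
- **Zero-change baseline rows.** Adding Week-0 rows with change fixed at 0 restores rank 5, and the slope then detects a 1-SD change about 95% of the time. The SAP does not state this. Such rows have no variance by construction, and a simplified least-squares version rejects about 6.5% under the null.
- **Time pattern.** The dose is raised at Week 4, so a full effect by then may be unlikely. This stands in part. With no effect at Week 4 and the full effect from Week 8, the slope rejects 98.5%; with none at Week 4 and a linear rise after, 99.8%. The loss for PROs is therefore specific to effects that appear early and level off.
- **Pilot status.** The study is descriptive and was not sized for power. That limits the weight of rejection rates, but Protocol 12.5 says its estimates will help power later studies, and for that mean changes with their CIs are needed.
- **Week 20 and safety.** Nothing says Week 20 enters the model, so that result is conditional. No continuous safety endpoint is named, though the SAP applies this model to continuous safety outcomes.

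**Conclusion.** The concern holds. For TGF-β, HSS and EndoFLIP the stated test is not estimable at nominal visit times, a matter of algebra that needs no assumption about the data. With actual dates or early leavers a slope can be computed, but it reflects timing differences between participants and carries almost no information on the drug effect (5% rejection against 94% for a uniform 1-SD change).

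For PROs and continuous safety measures the test addresses the wrong quantity. A held effect is missed whatever the SDs; partial early effects lose power; effects that build steadily or start after Week 4 are detected. The intermediate percentages rest on the assumed SDs, normal data and a 1-SD effect. The Week 20 result applies only if that visit is included.

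The eosinophil endpoint has its own mean-change CI and paired test, and SAE/Grade 3+ reporting is descriptive; neither is affected.

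**What to change.** 1. **TGF-β, HSS, EndoFLIP, and the transcriptome if scored continuously:** estimate and test mean change to EOT with a 95% CI, overall and by group, from the model change = group + centred baseline. The paired non-parametric test already specified for eosinophils could accompany it.
2. **PROs and continuous safety measures:** treat visit as categorical, test the Week-16 mean change from baseline against zero with a 95% CI, and give the EoE-CTD versus EoE difference at Week 16. Keep the slope as supportive.
3. **Visits:** state which enter the model, and report Week 20 separately as post-treatment.
4. **Paired tests:** say whether the overview sentence covers any outcome besides eosinophils.

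The cost is SAP wording only, with no new data; categorical visits use a few degrees of freedom. Precision follows the Table 7 method: in SD units the CI half-width is 2.77/5 = 0.55 (n = 15), 3.58/5 = 0.72 (n = 10) and 6.21/5 = 1.24 (n = 5), so the EoE-CTD estimates will be imprecise.
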